10.5. Primary and secondary outcome measures

- Primary outcome:
 - A change in pharmacokinetic parameters (C_{max} and AUC_{0-10}) of plasma analytes after treatment with a product made from a water extract of *Centella asiatica* (CAP) with a detectable difference between doses (2g and 4g).
- Secondary outcome:
 - The time of maximum concentration (t_{max}) and half-life ($t_{1/2}$) of the known bioactive compounds and their metabolites to help determine dosage intervals
 - Temporal changes in ferric reducing ability of plasma (FRAP) as an indicator of antioxidant potential over time
 - Safety and tolerability of acute doses of CAP determined by participant interviews, biometrics, electrocardiography, laboratory assessments of liver and kidney function, vital signs and questionnaires
 - The levels of triterpenes, caffeoylquinic acids, and their metabolites in a pooled urine sample collected over 10 h after CAP administration
 - Activation of the NRF2 antioxidant response element pathway in peripheral blood mononuclear cells (PBMC) over 6 hours following CAP administration.

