Sample collection: Participants will be asked to fast for 10 hours prior to each study visit, excluding water, in an attempt to standardize gastrointestinal transit time and minimize delayed absorption of the study intervention due to the presence of food. A study clinician or CTRC nursing staff member will place a peripheral intravenous catheter in the participant's arm or hand to allow for serial plasma specimen collection. Prior to administration of the *Centella asiatica* product, a baseline blood sample of one tablespoon (15 mL) will be collected through the catheter using a syringe and transferred immediately into a heparinized Vacutainer tube. The participant will be asked to consume by mouth one of the two doses of *Centella asiatica* product dissolved in 8-12 ounces of warm water, on an empty stomach in the presence of study personnel to ensure compliance. Participants will be asked not to consume food for two hours following consumption of the study intervention to allow for transition into the small intestine and absorption. If signs of hypoglycemia present, participants will be allowed to consume a high glycemic food and monitored for improvement. Serial blood samples (two or three teaspoons (10 -15 mL)/sample) will be obtained through the peripheral intravenous catheter using a syringe over a 10-hour post-administration period (15, 30, 45, 60, 90, 120, 150, 180, 240, 360, 480, and 600min) (Table 4). The 15 mL samples will be collected at 60, 120, 180, 240 and 360 mins to allow for 5 mL to be processed for PBMC isolation. Participants will collect their urine for the duration of the study visit (10 hours) to assess for excretion of *Centella asiatica* metabolites.

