9.2. Handling of data and specimens

Upon enrollment, each participant will obtain a unique identification number. This number will be associated with all specimens and data collected from that participant. Following the collection of whole blood from the participant, a trained member of the study team will transfer the blood to the specified Vacutainer tubes. Vacutainers containing a 5 mL aliquot of blood for NRF2 analysis from the screening (6.6) and study visits (6.9) will be transferred to [name] laboratory for isolation of PBMC and measurement of gene expression and/or protein levels related to NRF2 activation (in collaboration with [name], OHSU). For analysis of CA compounds, study staff will process the blood by centrifugation in the CTRC's laboratory to separate the plasma for analysis. The isolated plasma will be transferred into labeled tubes and placed on ice until transported by a member of the study team via a sealed Styrofoam cooler labeled with biohazard to The Oregon Alzheimer Disease Center Biomarker Core Lab (Biomedical Research Building, OHSU). The plasma and a 50mL aliquot of the urine specimens will be stored in labeled boxes in [name] -70°C freezer for up to five years. All written data will be stored in a locked cabinet in [name] office (Richard Jones Hall, OHSU) for up to five years. All computerized data will be stored in OHSU's installment of REDCAP and in a password protected folder on the OHSU X-drive for up to five years.

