9.3. Detection of *Centella asiatica* derived compounds in plasma and urine

Biological levels of *Centella asiatica* triterpenes, caffeoylquinic acids, and their metabolites will be assessed in both plasma and urine using high-performance liquid chromatography coupled to tandem mass spectrometry (HPLC-MS/MS). Plasma calibration curves will be made using pooled baseline human plasma from the study participants (one teaspoon (5 mL)/participant) separated by gender. The blank plasma will be spiked with increasing doses of commercially available reference triterpenes, caffeoylquinic acids and known metabolites, as well as appropriate internal standards (see below). If the blank plasma is found to contain traces of the analytes, we will calculate the true concentration by back extrapolation using the method of standard addition. A pooled baseline urine sample taken from participants (separated by gender) will be used as a "blank" urine sample for spiking with standards.

Triterpenes; Plasma (200 µl) and urine samples (3000 µl) will be mixed with phosphoric acid and internal standard (chrysin) before incubation with *E. coli* glucuronidase and *S. aerogene* sulfatase to release the analytes of interest from glucuronide and sulfate conjugates. Incubated samples are passed through a Supelco Supelclean™ C8 column, washed with dilute aqueous acetic acid to remove salts, and eluted with ammoniacal methanol. The eluant is vacuum dried, reconstituted in 200 µl of 1:1 methanol: ammonium acetate and filtered through a 0.2 µM spinfilter to remove residual particles before analysis. HPLC-MS/MS will be performed on an Applied Biosystems Q-Trap 4000 LC-MS instrument. The analytical method to be used is a modification of that described by Nair et al. (Nair, Menon et al. 2012) Chromatographic separation will be achieved using a Poroshell 120 EC18 column and methanol:ammonium acetate gradient. Triterpenes will be detected as their ammonium adducts with positive ion mode electrospray ionization using the following MS/MS transitions: AA (506/453) and MA (522/451), and chrysin will be detected as the molecular ion (255/255).

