10.6. Specimen analysis

Each CAP derived analyte will be identified by its retention time and characteristic mass spectral fragmentation pattern using selected reaction monitoring. The peak area ratio to the appropriate internal standard will be identified and evaluated against the standard calibration curve of each analyte. Each analyte's concentration will be used to generate a concentration-time curve for pharmacokinetic profiling. Pharmacokinetic (PK) profiling of the triterpenes, CQAs and their metabolites will use non-compartmental analysis (NCA) to calculate common PK parameters such as peak concentration (C_{max}), the time at peak concentration (t_{max}) and the total 10 hour bioavailability represented by the total area under the curve (AUC_{0-10}). These will be compared to the mouse data in order to assess appropriateness of dosing level. Other calculable NCA metrics will also be determined, such as the elimination half-life ($t_{1/2}$) calculated from the profile tails and the mean residency time (MRT) of the compounds in plasma. Descriptive assessment will be done at each of the doses to give basic PK summarization of the various CA compounds and total antioxidant compounds measured by FRAP. NRF2 antioxidant pathway related gene and/or protein levels will be compared in PBMCs from the screening visit, the baseline study visit sample and hourly up to 6h following CAP administration. Dose dependence of the study outcomes will be determined by evaluation of the within-subject differences in study outcomes between the 2g and 4g CAP doses.

Assumptions of normality will be confirmed using outcome density distributions alongside utility from formal tests, such as the Anderson-Shapiro. In instances of normality violation, statistical transformation such as natural logs and square roots will be considered as will non-parametric equivalent tests such as the paired Wilcoxon rank-sum test. Standard diagnostics will be very conservative given the limited number of available subjects but clearly obvious outliers will be removed as necessary. Non-continuous variables such as t_{max} will have frequency distributions compared between doses using chi-square testing. Although all CA compounds of interest and PK parameters are defined a priori, multiple comparison correction to p-values will be applied as necessary, with final two-tail significance defined at $p < 0.05$.

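### The 10-hour urine collection is meant to assess excretion, but the plan does not provide for total urine volume, so amount excreted cannot be calculated and the dose comparison loses precision

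*Combined protocol and SAP*

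**What the plan says.** All references are to the combined protocol and SAP.

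- **Purpose.** Section 6.9 (sample collection): "Participants will collect their urine for the duration of the study visit (10 hours) to assess for excretion of" *Centella* metabolites. Section 4.1 gives the same purpose.
- **Endpoint.** Section 10.5, and similarly 4.2: the levels of the analytes and their metabolites "in a pooled urine sample collected over 10 h after CAP administration". No unit is given.
- **Assay.** Section 9.3: analytes "will be assessed in both plasma and urine using high-performance liquid chromatography" with tandem mass spectrometry, using 3000 µl of urine. Under section 10.6 the signal is "evaluated against the standard calibration curve of each analyte", which returns a concentration.
- **Handling.** Section 9.2: "The plasma and a 50mL aliquot of the urine specimens will be stored in labeled boxes". No step before this measures the whole collection.
- **Dilution markers.** Table 5 limits study-visit urinalysis to baseline. No creatinine or specific-gravity correction is described.
- **Case report forms.** The study-visit form in Appendix 1 covers biometrics, vitals, ECG and safety tests, but no urine volume.
- **Comparison.** Section 10.6 judges dose dependence of the study outcomes by within-subject differences between the two doses.

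**The concern.** Excretion is an amount. A complete timed collection is worth its burden because concentration multiplied by total volume gives that amount. The plan sets up the collection and the assay but not the factor that joins them.

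Two things are at stake. First, the stated aim is out of reach: without volume there is no amount excreted, and nothing to set beside the coffee figure in section 2.4, where urinary metabolites corresponded to about 30% of intake. Second, concentration depends on how much a participant drank and voided that day. Fluid intake is not fixed: water is exempt from the fast, and no intake is set for the rest of the visit. The dosing fluid is 8-12 ounces in section 6.9 but 10-12 ounces in sections 5.1 and 5.7; these passages must be reconciled. Day-to-day dilution therefore enters the comparison of doses. If the rest of the collection is discarded unmeasured, the amount cannot be reconstructed.

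**Working it through.** The documents state no urine figure, power or variance, so there is nothing to reproduce for this endpoint. The steps below size the consequence.

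**Inputs from the documents:** n = 8 in a two-dose crossover with randomised order (4.1, 10.1); two-sided 5% level and within-subject comparison (10.6).

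**Assumptions, not in the documents:** true 4 g/2 g ratio of amount excreted 2 (proportional excretion), with 1.5 as a sensitivity case; within-subject CV of amount 30%; within-subject CV of 10-hour volume 20%, 30% or 50%; volume independent of dose and of amount.

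**1. Model.** Concentration = amount / volume, so for each participant

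log(concentration ratio) = log(amount ratio) − log(volume ratio).

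**2. SD of the log volume ratio** = √(2·ln(1+CV²)):
- CV 20%: √(2 × 0.0392) = 0.280
- CV 30%: √(2 × 0.0862) = 0.415
- CV 50%: √(2 × 0.2231) = 0.668

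**3. Effect of dilution on the group result.** The 95% factor for the geometric mean ratio over 8 participants is exp(1.96·SD/√8) = 1.21, 1.33 and 1.59.

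**4. Power.** Paired t-test on the log scale, noncentral t with 7 df, noncentrality = ln(2)·√8/SD, where SD = √(2·[ln(1+CV²amount) + ln(1+CV²volume)]).

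| Analysed quantity | SD | Noncentrality | Power, ratio 2 | Power, ratio 1.5 |
|---|---|---|---|---|
| Amount (volume known) | 0.415 | 4.72 | 98% | 66% |
| Concentration, volume CV 20% | 0.501 | 3.91 | 92% | 51% |
| Concentration, volume CV 30% | 0.587 | 3.34 | 82% | 39% |
| Concentration, volume CV 50% | 0.787 | 2.49 | 57% | 24% |

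(The noncentrality column is for ratio 2.) With the one dropout that section 10.8 expects (n = 7) and ratio 2, the powers are 95% on amount and 86%, 74% and 50% on concentration.

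**5. Share of variance.** Dilution supplies ln(1+CV²volume) / [ln(1+CV²amount) + ln(1+CV²volume)] of the variance of the log concentration ratio: 31%, 50% and 72% at the three volume CVs.

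**6. Bias.** In simulation with n = 8, amount CV 30% and volume CV 30% or 50%, the test on concentration rejected a true null in 5.1% and 4.9% of trials, and the estimated ratio was 2.00 for a true ratio of 2. Dilution unrelated to dose costs precision and does not shift the estimate.

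**The case against.** A reader might infer that volume is definitely not recorded. The documents do not say so; they are silent. Site staff may read the container as routine. That is a fair correction to the wording, but a number with no form field and no place in the endpoint definition is not part of the analysis plan.

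A reader might also infer that the dose comparison is driven by dilution rather than by excretion. That does not follow. Each participant is their own control, dose order is randomised, participants are blinded, and both doses carry the same excipients, so dilution has no evident reason to differ by dose. It becomes the larger variance component only if the volume CV exceeds the amount CV, and the documents give neither.

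Nor should the spread for one participant be set against a dose ratio of 2. At volume CVs of 20-50% it is a factor of 1.7 to 3.7, but the trial compares doses across 8 participants, where the factor is 1.2 to 1.6.

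The stakes are limited. Section 1.3 calls urine an additional endpoint, although 4.2 and 10.5 list it as secondary. No hypothesis in 10.4 concerns urine, and the sample size in 10.8 rests on plasma Cmax and AUC. Visits are also partly standardised by the fast, the fixed window and the supplied meals.

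A dilution marker could in principle be assayed later in the stored aliquot. No such step is planned, and it would not give the amount excreted.

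These points limit the size of the problem. They do not answer the mismatch between an excretion aim and an endpoint from which excretion cannot be calculated.

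**Conclusion.** The point holds as a gap between aim and endpoint, with a loss of precision. Followed as written, the plan cannot give amount excreted, and random dilution adds noise to the comparison of doses. At an assumed amount CV of 30%, true ratio of 2 and n = 8, power falls from 98% to between 92% and 57% as the volume CV goes from 20% to 50%. The loss is modest at the lower end of that range and material at the upper end. The CVs and the true ratio are assumptions, and the absence of bias rests on volume being unrelated to dose. The primary plasma Cmax and AUC comparison is untouched. It is worth correcting before collection starts, because an unmeasured volume cannot be recovered.

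**What to change.** 1. In sections 6.9 and 9.2, require total 10-hour urine volume or weight to be recorded before the 50 mL aliquot is taken.
2. Add the corresponding field to the study-visit case report form in Appendix 1.
3. In sections 4.2 and 10.5, define the endpoint as amount excreted over 0-10 h (concentration × total volume). In section 10.6, compare that amount between doses within participants.
4. Treat percent of dose excreted as optional. It needs the assayed content of the product, and the documents do not settle this: section 2.5.4 gives about 4% triterpenes for CAP, while section 3.1 gives 0.94-2.41% for the water extract. The denominator could thus differ by a factor of 4/2.41 = 1.7 to 4/0.94 = 4.3. It also needs a baseline correction, since section 10.3 notes that these compounds, particularly the caffeoylquinic acids, may come from the diet.

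The cost of items 1 to 3 is one measurement per visit of a container already collected, one form field and a few sentences of text.

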10.6. Specimen analysis

Each CAP derived analyte will be identified by its retention time and characteristic mass spectral fragmentation pattern using selected reaction monitoring. The peak area ratio to the appropriate internal standard will be identified and evaluated against the standard calibration curve of each analyte. Each analyte's concentration will be used to generate a concentration-time curve for pharmacokinetic profiling. Pharmacokinetic (PK) profiling of the triterpenes, CQAs and their metabolites will use non-compartmental analysis (NCA) to calculate common PK parameters such as peak concentration (C_{max}), the time at peak concentration (t_{max}) and the total 10 hour bioavailability represented by the total area under the curve (AUC_{0-10}). These will be compared to the mouse data in order to assess appropriateness of dosing level. Other calculable NCA metrics will also be determined, such as the elimination half-life ($t_{1/2}$) calculated from the profile tails and the mean residency time (MRT) of the compounds in plasma. Descriptive assessment will be done at each of the doses to give basic PK summarization of the various CA compounds and total antioxidant compounds measured by FRAP. NRF2 antioxidant pathway related gene and/or protein levels will be compared in PBMCs from the screening visit, the baseline study visit sample and hourly up to 6h following CAP administration. Dose dependence of the study outcomes will be determined by evaluation of the within-subject differences in study outcomes between the 2g and 4g CAP doses.

Assumptions of normality will be confirmed using outcome density distributions alongside utility from formal tests, such as the Anderson-Shapiro. In instances of normality violation, statistical transformation such as natural logs and square roots will be considered as will non-parametric equivalent tests such as the paired Wilcoxon rank-sum test. Standard diagnostics will be very conservative given the limited number of available subjects but clearly obvious outliers will be removed as necessary. Non-continuous variables such as t_{max} will have frequency distributions compared between doses using chi-square testing. Although all CA compounds of interest and PK parameters are defined a priori, multiple comparison correction to p-values will be applied as necessary, with final two-tail significance defined at $p < 0.05$.

Incidences of adverse events, both overall and within distinct organ systems, will be compared across treatment arms using Fisher's Exact test. Pairwise examination will test for significant differences in rates between each CAP dose..

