10.2. Reason for randomization

The order in which the doses are administered will be randomized so that some data will be available for both doses in case of dropouts after the first visit. It is also randomized to prevent a tolerance effect.

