10.8. Sample size

Sample size was calculated based on the primary outcome measures of C_{max} and AUC. Changes in the response values from the literature were taken from Grimaldi et. al.⁴⁵ for two outcomes, peak concentration (C_{max}) and bioavailability/area-under-the-curve (AUC), at two treatment doses. With respect to C_{max} , estimations from G*Power indicated a sample size of 6 would be sufficient to detect the established criterion difference (critical $t=2.57$).

The post-treatment mean difference in C_{max} from the literature was found to be 0.66 and was replicated during simulation with confidence intervals indicating a significant difference {0.36, 0.96}. Both the observed mean and median test statistics was found to be greater than the critical t (mean $t=4.23$, median $t=3.88$). Mean power was found to be slightly lower than expected (84% versus 86%) although median power was significantly larger (92%). Accordingly, six subjects would be sufficient to detect a difference in C_{max} between two doses of CAP. With the enrollment of 8 subjects, the study will be sufficiently powered even with a dropout rate of 25%.

Similar results were found for bioavailability, as measured as AUC, although at an attenuated effect, with an indicated increase in subject count to a minimum of 7 (critical $t=2.45$). Simulation verified a mean difference of 5.25 that would be expected to be significant based on the simulated confidence intervals {2.43, 8.09}. AUC was also found to be similarly powered, with a mean observed power of 83% and a median power of 93%. Accordingly, a sample size of seven is more than sufficient to meet the proposed criterion for CAP analyte bioavailability. With the enrolment of 8 subjects, the study will be sufficiently powered with 1 dropout (14%). Given the short duration of the study, we expect that a dropout rate of only 1 subject is reasonable. Eight total subjects were proposed for the dose comparison of Aim 1, which would allow for reductions in the detectable shifts of both peak concentration (37% of literature effect; $\Delta C_{max}=0.42$) and bioavailability (31% of literature effect; $\Delta AUC=3.63$) allowing for even greater powering to detect a dose effect of CAP.

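### The 2g versus 4g comparison of Cmax and AUC0-10 is planned as a plain paired difference with no period term, although dose order is randomised partly to guard against an order effect

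*Combined protocol and SAP*

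**What the plan says.** The primary outcome (sections 4.2 and 10.5) is the change in Cmax and AUC0-10, with a detectable difference between 2g and 4g. For that comparison section 10.6 states: "Dose dependence of the study outcomes will be determined by evaluation of the within-subject differences in study outcomes" between the two doses. If normality fails it allows transformation or "non-parametric equivalent tests such as the paired Wilcoxon rank-sum test". Neither the main method nor the fallback carries a term for visit or order, and no section names a period, sequence or carryover term, a mixed model, or a rule for a missing visit.

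Sections 5.6 and 10.2 randomise dose order so that "some data will be available for both doses in case of dropouts after the first visit". Sections 5.2 and 10.2 give a second reason, prevention of a tolerance effect. Section 5.6 aims for equal numbers in each order.

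Section 10.8 sizes the trial at n=6 for Cmax (critical t 2.57) and n=7 for AUC (critical t 2.45). Sections 4.3.1 and 10.8 treat dropouts as lost to the comparison: eight enrolled, falling to seven or six.

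**The concern.** The second reason for random order concedes that the response might differ between the first and second visit. The visits are two to four weeks apart, and each follows a self-managed 48-hour diet. Random order balances a visit effect on average. It does not remove that effect from the within-person differences: it pushes them up in one order and down in the other, and a plain paired test counts this spread as noise. If dropout leaves the orders unequal, the visit effect no longer cancels and shifts the dose estimate.

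At stake is the power and precision of the primary dose comparison. A smaller matter is that a participant with visit 1 only has no within-person difference, so the comparison cannot use the data that random order was partly meant to protect.

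**Working it through.** **1. The plan's own figures.** Two-sided alpha is 0.05 (section 10.6). With n-1 df, t(0.975, 5) = 2.571 and t(0.975, 6) = 2.447, which match the stated 2.57 and 2.45. A period-adjusted 2x2 analysis has n-2 df: t(0.975, 4) = 2.776 and t(0.975, 5) = 2.571. The sample size therefore rests on an unadjusted paired test.

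**2. Effect sizes (assumed).** Section 10.8 gives a Cmax mean difference ("mean difference in C_{max} from the literature was found to be 0.66") but no SD of the within-person difference, so the stated power cannot be recomputed directly. Solving the noncentral t with noncentrality dz × √n for the stated power gives dz = 1.56 for Cmax (86% at n=6) and dz = 1.33 for AUC (83% at n=7). At n=8 these give 96% and 89% for the plain test.

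**3. Effect of a period effect.** Let d = 4g minus 2g, with dose effect τ, within-order SD σ, and period effect π (visit 2 minus visit 1). Then E(d) = τ + π in the 2g-first order (n1 people) and τ − π in the 4g-first order (n2 people).

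- The plain mean estimates τ + π(n1 − n2)/(n1 + n2). The bias is 0 at 4/4 and 3/3, π × 1/7 at 4/3, and π × 2/6 = π/3 at 4/2.
- At 4/4 the expected sample variance of d is σ² + (8/7)π². For π = 0.5σ it is 1.29σ²; for π = 1.0σ it is 2.14σ².
- The adjusted estimate is half the sum of the two order means, with SE = (σ/2)√(1/n1 + 1/n2). It does not depend on π.

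**4. Simulated power at 4/4** (100,000 to 200,000 trials per setting; π is assumed, in SDs of d):

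| π | Cmax plain | Cmax adjusted | AUC plain | AUC adjusted |
|---|---|---|---|---|
| 0 | 96% | 95% | 89% | 88% |
| 0.25 | 96% | 95% | 88% | 88% |
| 0.5 | 93% | 95% | 83% | 87-88% |
| 1.0 | 79-80% | 95% | 62% | 87-88% |

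With no dose effect, the plain test rejects 2.9% of the time at π = 0.5 and 0.7% at π = 1.0 (4/4). At 4/2 the figures are 4.3% and 2.5%. It is conservative, and false positives were not inflated in any setting tried.

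**5. Cost of adjusting when π = 0** (power, plain to adjusted):

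| Orders | Cmax | AUC |
|---|---|---|
| 4/4 | 96.4 to 95.4 | 89.3 to 87.5 |
| 4/3 | 92.8 to 90.0 | 83.0 to 79.0 |
| 3/3 | 86.0 to 81.3 | 73.8 to 68.4 |
| 4/2 | 86.0 to 76.9 | 73.8 to 63.6 |

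**6. Recovering single-visit participants.** By generalised least squares with dose and period terms, known variances and an assumed within-person correlation from 0 to 0.9, the SE of the dose effect falls by 3.9% down to 0.4% for seven complete plus one single-visit. For six complete plus two, one lost from each order, it falls by 7.4% down to 0.8%. The higher the correlation, the smaller the gain.

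**The case against.** The strongest reply is that the plan is silent rather than wrong. Section 10.6 names no parametric model, and the period-adjusted crossover estimate is itself built from within-person differences, so the wording does not exclude it. That stands as far as it goes. But the n-1 degrees of freedom and the paired fallback make the unadjusted reading the natural one, and an eight-person primary comparison should not leave the choice open.

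A reader might infer that the plan throws away visit-1-only participants and so contradicts its reason for randomising. The documents do not support that. Section 10.2 promises only some data on both doses, and section 10.6 provides descriptive PK summaries at each dose and a comparison with the mouse data. Such a participant can contribute to both. The adverse-event comparison is not restricted to completers either. The loss is confined to the dose comparison, and step 6 shows it is small.

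A reader might also infer a biased test or excess false positives. With balanced orders there is no bias, and the test is conservative. The one-third bias needs two dropouts, both from the same order, whereas section 10.8 regards one dropout as reasonable.

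Finally, no period effect is documented. Both visits use the same diet, fast and supervised dosing (section 6.9), and section 10.3 compares pre-dose levels between visits. That comparison addresses washout, not a period effect, but the sizes used here remain assumptions. A smaller dose effect would make the loss look worse: at an assumed standardised difference of 1.25 and π = 1.0 SD, plain power is about 55% against 84% adjusted. The documents do not give 1.25, and their stated power implies larger values.

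**Conclusion.** The point holds as a moderate, inexpensive improvement to the primary dose comparison. The plan randomises order partly because of a possible order effect, then specifies an analysis that does not account for one. The harm under balance is lost power and too wide an interval. The loss is negligible at a period effect of 0.25 SD, about 2 points for Cmax and 4-5 for AUC at 0.5 SD, and about 15 and 25 points at 1.0 SD. Bias arises only if dropout unbalances the orders.

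These sizes rest on effect sizes back-solved from the stated power, assumed period effects and a 4/4 split. Adjustment does not always raise power: after dropout with no period effect it lowers it, and at 4/2 it gives up about 10 points for an unbiased estimate. Losing single-visit participants from the comparison is a secondary matter and would not justify the change alone.

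**What to change.** In section 10.6, make the primary dose comparison of Cmax and AUC0-10 a crossover mixed model with fixed dose, period and sequence and a random participant effect. Include every dosed participant, whether or not both visits were completed. Keep the simple paired difference as a sensitivity analysis. In section 10.8, restate power on n-2 degrees of freedom for eight, seven and six completers, and give the SD of the within-person difference used.

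The change is SAP wording only and needs no new data, visits or participants. It should be settled before unblinding, since adding a period term after seeing eight people's results would be a post hoc choice on the primary outcome. If there is no period effect, the cost is about 1-2 power points at 4/4, about 3-6 at 4/3 or 3/3, and about 10 at 4/2. Log-scale analysis with a geometric mean ratio is a separate, optional matter, because section 10.6 already allows a log transformation.
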